5.6.1.1. Definition of Endpoint(s)

Endpoint	Endpoint definition
Time to SARS-CoV-2 virus no longer detectable	A subject is considered as having an infection if the case is classified as mild, moderate or severe. For each subject the time to “SARS-CoV-2 virus no longer detectable” is the time between the onset of the COVID-19 episode and the first sample that is negative and after which no positive sample was observed. For this assessment only centrally confirmed assessments will be taken into account. The precision of this difference will be in Days, defined as the Day of the episode where this criterion is met (e.g., if the first sample that was negative was on Day 12 of the episode, the time to no longer detectable will be set at 12 Days).
Peak viral load	A subject is considered as having an infection if the case is classified as mild, moderate or severe. The peak viral load is defined as the highest viral load that was observed during a COVID-19 episode. For this assessment only centrally confirmed assessments will be taken into account.
Viral load over time	A subject is considered as having an infection if the case is classified as mild, moderate or severe. For this assessment only centrally confirmed assessments will be taken into account. For each assessment the viral load will be categorized to the two day schedule, where the first value will define the series. If a viral load is available before and after a scheduled day, the average on the \log_{10} scale will be used. If only one value is available in an adjacent day this value will be used.
ok	A subject is considered as having an infection if the case is classified as mild, moderate or severe. The first viral load is defined as the first viral load that was observed within a COVID-19 episode. For this assessment only centrally confirmed assessments will be taken into account.

The additional endpoints on viral load by quantitative RT-PCR are defined above and will be analyzed descriptively for all symptomatic cases separately by severity (all symptomatic infections, mild, moderate to severe/critical) as well as asymptomatic cases collected via PCR on the baseline and unblinding visits.

Assessment of the efficacy of Ad26.COV2.S in the prevention of SARS-CoV-2 infection (both symptomatic and asymptomatic infections combined, that are serologically and/or molecularly confirmed), as compared to placebo by first occurrence of SARS-CoV-2 infection (serologically and/or molecularly confirmed) from Day 1 to Day 29.

First occurrence of any health care utilization linked to any molecularly confirmed COVID-19. Health care utilization is defined as any event such as hospitalization, ICU admission, ventilator use linked to any molecularly confirmed COVID-19 at least 14 days and 28 days after double-blind vaccination.

Assessment of the efficacy of Ad26.COV2.S in the prevention of SARS-CoV-2 infection in participants with comorbidities associated with increased risk of progression to severe COVID-19, as compared to placebo defined as first occurrence of SARS-CoV-2 infection (serologically and/or molecularly confirmed) in participants with comorbidities associated with increased risk of progression to severe COVID-19 with onset at least 28 days after double-blind vaccination with study vaccine.

To explore the effect of Ad26.COV2.S on other potential complications of COVID-19 (linked to any respiratory disease and linked to any molecularly confirmed COVID-19) not previously described, as compared to placebo by first occurrence of potential complications of COVID-19 linked to any respiratory disease and linked to any molecularly confirmed COVID-19, with onset at least 14 days and at least 28 days after double-blind vaccination with study vaccine.

To explore the effect of Ad26.COV2.S on all-cause mortality, as compared to placebo by deaths occurring at least 14 days and at least 28 days after double-blind vaccination with study vaccine.

To evaluate the immune response in participants with COVID-19 in relation to risk of development of COVID-19, protection induced by Ad26.COV2.S, and risk of accelerated disease by assessment of the correlation of humoral immune responses with emphasis on neutralizing, binding and functional antibodies, as well as gene transcript profiling (RNA sequencing), with the risk of COVID-19 and protection induced by the study vaccine.

In a subset of participants to further assess the humoral immune response to Ad26.COV2.S, as compared to placebo for functional and molecular antibody characterization including, but not limited to avidity, Fc-mediated viral clearance, Fc characteristics, Ig subclass, IgG isotype, antibody glycosylation, and assessment of antibody repertoire, adenovirus neutralization as measured by VNA, analysis of antibodies to S and the receptor-binding domain (RBD) of the SARS-CoV-2 S protein and SARS-CoV-2 neutralization as measured by virus neutralization assay (VNA; wild-type virus and/or pseudovirion expressing SARS CoV-2 S protein).

To explore changes in the SARS-CoV-2 genome by development of SARS-CoV-2 variants

To evaluate patient-reported outcomes (PROs) in relation to the presence of SARS-CoV-2 infection and the presence, severity and duration of COVID-19 signs and symptoms in participants who received Ad26.COV2.S, as compared to placebo by presence, severity and duration of COVID-19 signs and symptoms and confirmation of SARS-CoV-2 infection by molecular testing.

To assess the difference in severity of cases in participants who received Ad26.COV2.S as compared to placebo by reduction in severity of COVID-19 signs and Symptoms

To assess the impact of pre-existing humoral immunity against coronaviruses other than SARS-CoV-2 at baseline on Ad26.COV2.S vaccine immunogenicity.

To assess the incidence of co-infection of COVID-19 and other respiratory pathogens and to assess the effect of the vaccine during such co-infections as well as to estimate the incidence of other respiratory pathogens during the study period.

To assess the frailty index in participants who received Ad26.COV2.S as compared to placebo.

5.6.1.2. Analysis Methods

For the assessment of the SARS-CoV-2 viral load by quantitative RT-PCR, in participants with molecularly confirmed, mild COVID-19 by serial viral load measurements during the course of a COVID-19 episode the analysis method as described in section [5.5.4.5](#) will be repeated limited to the molecularly confirmed, mild COVID-19 cases. To compare viral load of the asymptomatic cases at the unblinding visit between the active and placebo groups, with the exact Wilcoxon test. Descriptive statistics of the viral load will be calculated and box plots will be created for the active and the placebo group.

The number of days with detectable levels of viral load will be compared between vaccination groups and descriptively summarized. A non-parametric test may be employed to compare a shift in distribution.

For the first occurrence of any health care utilization linked to any molecularly confirmed COVID-19 defined as any event such as hospitalization, ICU admission, ventilator use linked to any molecularly confirmed COVID-19 at least 14 days and 28 days after double-blind vaccination, the proportion of participants will be tabulated and the VE as described in appendix 8 will be computed with the 95% exact CIs. If possible the impact of age group and comorbidities (as defined by the CDC, section [6.7](#)) will be investigated. If enough cases per event type are available (more than 6) a separate model can be performed per event type.

For the assessment of the efficacy of Ad26.COV2.S in the prevention of SARS-CoV-2 infection (both symptomatic and asymptomatic infections combined, that are serologically and/or molecularly confirmed), as compared to placebo by first occurrence of SARS-CoV-2 infection (serologically and/or molecularly confirmed) with onset at least 28 days after double-blind vaccination with study vaccine the analysis method as described in section 5.3 will be repeated using all SARS-CoV-2 infections. This analysis will be done using the PP and will be repeated in

the FAS for participants with comorbidities associated with increased risk of progression to severe COVID-19 (as defined by the CDC, section [6.7](#)).

For the assessment of the effect of Ad26.COV2.S on other potential complications of COVID-19 (linked to any respiratory disease and linked to any molecularly confirmed COVID-19) not previously described, as compared to placebo by first occurrence of potential complications of COVID-19 linked to any respiratory disease and linked to any molecularly confirmed COVID-19, with onset at least 14 days and at least 28 days after double-blind vaccination with study vaccine the proportion of participants will be tabulated and the VE as described in appendix 8 will be computed for the vaccine versus placebo with an associated 95% CI. If possible the impact of age group and comorbidities (as defined by the CDC, section [6.7](#)) will be investigated.

For the assessment of the effect of Ad26.COV2.S on all-cause mortality, as compared to placebo by deaths occurring at least 14 days and at least 28 days after double-blind vaccination with study vaccine, the proportion of participants will be tabulated and the VE as described in appendix 8 will be computed for the vaccine versus placebo with an associated 95% confidence interval. If possible the impact of age group and comorbidities (as defined by the CDC, section [6.7](#)) and age group will be explored. All-cause deaths occurring will be summarized by Kaplan-Meier method, and KM plot will be provided. In addition, summary will be provided for COVID-19 related deaths versus other reasons.

For the evaluation of the immune response in participants with COVID-19 in relation to risk of development of COVID-19, protection induced by Ad26.COV2.S, and risk of accelerated disease by assessment of the correlation of humoral immune responses with emphasis on neutralizing, binding and functional antibodies, as well as gene transcript profiling (RNA sequencing), with the risk of COVID-19 and protection induced by the study vaccine participants with a COVID-19 episode immunogenicity data will be tabulated by vaccine regimen at baseline, 28 days post double-blind vaccination, on COVID-19 Day 3-5 and on COVID-19 Day 29 for the standard immunogenicity assays (S-ELISA and VNA) and on COVID-19 Day 3-5 and on COVID-19 Day 29 for all other assays that are available ([Table 9](#)). Immunogenicity data will be graphically displayed by vaccine regimen where actual values are shown as dot plots with dots for participant values, and the corresponding geometric mean and 95% CI per time point for each assay. Correlates will be assessed in a subset where immune responses and transcriptome modifications are measured in all vaccine recipients who experience a SARS-CoV-2 event, and in random samples of vaccine recipients who have not been infected. These analyses will be described in a separate correlates SAP for this purpose.

For the assessment of the humoral immune response to Ad26.COV2.S, as compared to placebo for functional and molecular antibody characterization including, but not limited to avidity, Fc-mediated viral clearance, Fc characteristics, Ig subclass, IgG isotype, antibody glycosylation, and assessment of antibody repertoire, adenovirus neutralization as measured by VNA and analysis of antibodies to the receptor-binding domain (RBD) of the SARS-CoV-2 S protein refer to section [5.8.1](#).

Changes in the SARS-CoV-2 genome are focused at analyses of the S protein sequence. The presence of predefined viral variants will be tabulated. Further detail on vaccine efficacy by viral variant is described in section 5.8.2.6. Sequence analyses will be reported in a separate report. Time to resolution of COVID-19 episodes will be described for participants in the Ad26.COV2.S and placebo groups, using the Kaplan-Meier methodology, and if applicable compared with a logrank test.

For the medical intervention endpoint, a descriptive summary will be provided by type of intervention (as indicated by the adjudicators). A severity adjusted analysis will be done on the medical intervention endpoint (mechanical ventilation and ECMO, ICU, hospitalization).

A frailty index will be calculated at baseline and during the study at certain timepoints. The frailty index will be assessed in participants who received Ad26.COV2.S as compared to placebo.

The concordance between PCR results at an individual level as well as case level from various labs will be compared. For subjects with a PCR+ test result, a comparison will be done versus the subsequent serological result and the time to detect antibody levels since the positive PCR.

5.6.1.3. Vaccine efficacy on symptoms and reduction of severity

The analysis on whether the vaccine will reduce the severity of COVID-19 once participants are infected compared to placebo will be examined in 3 parts: reduction of severity based on case definitions, reduction of severity of any symptoms and reduction of lingering of symptoms. In a separate section the relation between viral load and symptom reduction and pattern will be characterized.

Based on case definitions

To assess whether there is a shift in severity of cases between the vaccine group and the placebo group a proportional odds model will be applied with associated p-value and confidence interval. The different severities of cases going from asymptomatic, mild, moderate to severe (further subcategories can be defined) are the ordinal categories used in the analysis. Barchat plots are used to present the shift in severity of cases between vaccinations groups

Additionally to the BOD model described above, a Burden of infection model (BOI) may be explored. In this analysis, asymptomatic cases, mild, moderate and severe cases are considered. A weighted-adjusted analysis for more severe cases will be implemented as 0 for asymptomatic, 1 for mild, 2 for moderate and 3 for severe cases.

Furthermore, analyses will be done that evaluates how many signs/symptoms as part of the definition were met during the episode. This will be graphically compared between randomized groups by severity (mild, moderate, severe). To investigate if vaccinated subjects experience less symptoms as part of the definition of a severe case and separately of a moderate case compared to placebo, VEs will be calculated by number of symptoms met as part of that definition. Further exploration of the moderate cases will be done to possibly identify subcategories (less severe moderate cases versus more severe moderate cases) using the number of symptoms reported as

part of the definition, the severity grade of the symptoms reported and the tier definitions as used for the adjudications (see Charter). This further exploration will be done to characterize the distribution of symptoms and severity among all moderate cases, and will be compared between vaccination groups.

Based on any symptoms

To evaluate if the vaccine induces a reduction of severity, the patient-reported outcomes (PROs) in relation to the presence of SARS-CoV-2 infection across case definitions are investigated. The presence, severity and duration of COVID-19 signs and symptoms are captured in multiple scores and statistics as described in section 5.8.4 and are compared for subjects with a SARS-CoV-2 infection between the vaccine group and the placebo group. Mean differences of scores and statistics are tabulated as well as graphically presented. Additionally, examination of the severity of symptoms over time will be done graphically by presenting symptom scores over time and will be used to explore differences in severity profiles over time between vaccination groups. A Markov multistate chain analysis on the severity changes over time may be applied to compare between vaccinated and placebo group with an associated p-value and confidence intervals .

Furthermore an analysis of the composite scores of the PROs will be done to possibly depict stronger reduction of severity of certain specific domains of symptoms for vaccinated subjects versus placebo subjects.

Lingering of symptoms

Time to resolution of symptoms will be presented by a Kaplan-Meier curve for participants in the Ad26-CoV-2 and placebo groups and will be compared with a log rank test with associated p-value and confidence interval if applicable. This analysis will be supplemented by time to resolution of domain specific symptoms using the composite scores as described in section 5.8.4

Relation between viral load and symptom reduction and pattern

Furthermore the association between viral load and symptoms may be explored graphically as well as via longitudinal modeling, at an individual level and a population level

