3.5.3. Asymptomatic infections and all infections (including asymptomatic)

Based on assumptions prior to unblinding the cases in the placebo group were assumed to be distributed as follows: 45% asymptomatic cases and 55% symptomatic cases of which 20% were mild infections, and 60% were moderate and 20% were severe infections, according to the case definitions. Based on a VE as detailed in [Table 4](#), events were simulated according to a binomial distribution and the primary endpoints evaluated against the SPRT boundary.

Upon crossing the SPRT boundary, the power against asymptomatic or undetected infections as well as against the evaluation of all infections was calculated (null hypothesis $VE>0$). The alpha level for that evaluation was adjusted according to the procedure detailed in the statistical hypothesis evaluation.

The results are based on 1000 simulations. The powers presented are not conditional on passing the first 2 secondary hypotheses.

Table 4 Powers for Asymptomatic and All Infections for various Fractions of available N-Elisa samples at 2.5 months at the time of analysis

Fraction of available N-Elisa samples At 2.5 months	Vaccine efficacy			Power		
	Moderate/Severe	Mild	Asymptomatic	Moderate/Severe	Asymptomatic	All infections
100%	70%	60%	30%	99%	14%	96%
100%	70%	60%	40%	99%	28%	99%
100%	70%	60%	50%	99%	47%	>99%
50%	70%	60%	30%	99%	4%	99%
50%	70%	60%	40%	99%	7%	>99%
50%	70%	60%	50%	99%	13%	>99%

This is based on the protocol assumed incidence of 1.4% during 3 months and waning thereafter (by 50% in Month 4, by 62% in Month 5 and beyond) and a sample size of 60,000.

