5.5.4.5. AUC viral load

To compare VL-AUC after infection between the active and placebo groups, the exact Wilcoxon Rank Sum test will be performed.

Values below the LLOQ will be imputed with 1 when detected and with 0 when not detected.

These imputations will be used when calculating the AUC based on equation (1). In addition, in case some observations are missing at the first timepoint after infection and/ or the last timepoint after challenge, missing values should be imputed with 0. No other missing values will be imputed.

AUC-VL values will be descriptively summarized (mean, median, SD, SE, range) by randomized group and COVID-19 severity (all symptomatic infections, mild, moderate to severe/critical).

Individual profiles of viral load over time and $\log_{10}[\text{viral load}]$ over time since onset of a COVID-19 episode will be summarized by randomized group and severity of COVID-19.

The vaccine efficacy against AUC-VL will be estimated through the geometric mean ratio of AUC-VL with associated 95% confidence interval.

As the comparison of the AUC VL after infection between the active and placebo groups is based on post-randomization groups, this analysis may not assess the causal effect of the vaccine on viral load. A sensitivity analysis as described by Gilbert et al. (2003) will be carried out. In this sensitivity analysis, a logistic selection bias model is employed to define a causal estimator for the vaccine effect on viral load. The unknown slope (b) of this logistic model determines the amount of selection bias; b is varied over a plausible range of values. For each value of b , a non-parametric estimate of the causal vaccine effect is calculated. A confidence interval and p-values for the appropriate hypothesis of interest are obtained by bootstrap. If $b < 0$, there is a selection bias towards a lower viral load in the vaccine group as compared to the placebo group. When $b = 0$, no selection bias is assumed. The hypothesis of interest is the one-sided hypothesis of a reduction of the viral load. Therefore, values of $b \leq 0$ will be considered (from -5 to 0 in steps of 0.01). The estimate of the causal vaccine effect with its $100*(1-2*\alpha)$ % confidence interval and the p-value for the one-sided hypothesis of a viral load reduction in the vaccine group will be plotted against the assumed value of b .

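### The severity-shift tests in SAP 5.6.1.3 compare infected participants only, so selective prevention alone can look like milder disease, and the SAP's own safeguard for viral load is not applied to them

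*SAP*

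**What the plan says.** SAP section 5.6.1.3 introduces its analyses as examining "whether the vaccine will reduce the severity of COVID-19 once participants are infected compared to placebo". For the case definitions, the purpose and the model are given as: "To assess whether there is a shift in severity of cases between the vaccine group and the placebo group a proportional odds model". The same sentence goes on to say that "a proportional odds model will be applied with associated p-value and confidence interval", on ordinal categories "going from asymptomatic, mild, moderate to severe". Being uninfected is not one of the levels.

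For symptoms, patient-reported scores "are compared for subjects with a SARS-CoV-2 infection between the vaccine group and the placebo group". The mean differences are tabulated and plotted, and an optional Markov multistate comparison carries a p-value. For lingering symptoms, the Kaplan-Meier curves of time to resolution "will be compared with a log rank test with associated p-value and confidence interval if applicable".

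Section 5.5.4.5 makes the same kind of comparison for viral load, but adds a caution. Because that comparison is "based on post-randomization groups, this analysis may not assess the causal effect of the vaccine on viral load", it plans a sensitivity analysis with a logistic selection-bias model whose slope b runs from -5 to 0. Section 5.6.1.3 has neither the caution nor the analysis.

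**The concern.** Infected vaccinees are the people the vaccine did not protect. Infected placebo recipients include people like them and also people the vaccine would have protected. Randomization balances the arms as a whole, not these two subsets. If protection is stronger in people who would have had a more severe infection, the infections left in the vaccine arm are milder on average, although none of them was changed.

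The proportional odds test therefore answers whether case mix among the infected is the same in both arms, which amounts to asking whether vaccine efficacy is equal at every severity. The section's opening question is about something else: whether an infection that still occurs is made milder. At stake is a reported finding of milder disease once infected, with a p-value, that selection alone could have produced.

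**Working it through.** **The plan's own figures.** The SAP gives no operating characteristics for the severity-shift test. As a check on the common inputs (1:1 allocation, 154 events), an exact binomial recursion over the efficacy boundary reproduces the primary design: type I error 0.023976 and power 0.862198 at VE 60%, against the stated 2.398% and 86.22%.

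**Inputs.**
- Placebo case mix (3.5.3): "45% asymptomatic cases and 55% symptomatic cases of which 20% were mild infections", with 60% moderate and 20% severe. As shares of all infections: asymptomatic 0.45, mild 0.55 × 0.20 = 0.11, moderate 0.55 × 0.60 = 0.33, severe 0.55 × 0.20 = 0.11.
- Efficacies (Table 4): moderate/severe 70%, mild 60%, asymptomatic 30%, 40% or 50%.
- Size: 154 moderate or severe events (3.1). The number at the final double-blind analysis is not given, so 77 and 308 were also run.
- Assumptions: every efficacy acts by preventing infection and no infection changes severity; two-sided 5%, since 5.6.1.3 states no level; Poisson counts; all asymptomatic infections detected.

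**Expected case mix, first Table 4 row.** Vaccine count relative to placebo = share × (1 - VE):
- asymptomatic 0.45 × 0.70 = 0.315
- mild 0.11 × 0.40 = 0.044
- moderate 0.33 × 0.30 = 0.099
- severe 0.11 × 0.30 = 0.033
- total 0.491

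Dividing by 0.491, the vaccine mix is 64/9/20/7%, against 45/11/33/11% on placebo. No infection has been softened.

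**Why the test cannot tell the two explanations apart.** Suppose instead that the vaccine prevents 50.9% of infections regardless of would-be severity. Per placebo infection, the remaining shares would be 0.491 × (0.45, 0.11, 0.33, 0.11) = 0.221, 0.054, 0.162, 0.054. Moving some of these down a level or more gives exactly 0.315, 0.044, 0.099, 0.033: at least mild falls from 0.270 to 0.176, at least moderate from 0.216 to 0.132, severe from 0.054 to 0.033. Softening and selective prevention then give the same expected counts.

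**Size of the effect.** At 154 moderate or severe events, placebo has 154/1.30 = 118.5 of them, so 118.5/0.44 = 269 infections. The vaccine arm has 269 × 0.491 = 132. The test was simulated as the tie-corrected Wilcoxon test, which is the score test of the two-group proportional odds model (20,000 to 40,000 simulations). Rejection with no softening at all:

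| VE asymptomatic / mild / moderate-severe | 77 events | 154 events | 308 events |
|---|---|---|---|
| 30/60/70% (Table 4) | 72% | 95% | 99.9% |
| 40/60/70% (Table 4) | 52% | 82% | 98% |
| 50/60/70% (Table 4) | 30% | 53% | 82% |
| 60/65/70% (small gradient) | 12% | 19% | 34% |
| 65/68/70% (smaller still) | 7% | 9% | 13% |
| equal at every severity | 5% | 5% | 5% |
| Table 4, symptomatic cases only | 7% | 10% | 14% |
| 70/70/50% (reversed gradient) | 27% | 47% | 76% |

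Virtually all rejections in the Table 4 rows point to milder disease; in the reversed row they point to more severe disease. Two checks on the first row at 154 events: a fitted proportional odds model rejects 97% (150 simulations), and a two-proportion power formula for the symptomatic share, 0.55 against 0.36, gives 96%.

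**Whether the SAP's own method would expose this.** Placebo cases were reweighted by a logistic selection model on severity scored 0 to 3, in the manner of 5.5.4.5 (154 events, 300 simulations). In the 30% row, rejection is 94% at b = 0 and 5% at b = -0.71, the slope that matches pure prevention. In the 50% row it is 53% at b = 0 and 4% at b = -0.36. Both slopes lie inside the range of -5 to 0 already used for viral load.

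**The case against.** The best defence is that the section is exploratory, outside the confirmatory hierarchy, and that the proportional odds sentence promises only a shift in case severity between arms, which is what the model tests. The randomized evidence is also already planned: severity-specific VE and the burden-of-disease score (5.5.4.2), and within 5.6.1.3 itself the VEs by number of symptoms and the optional burden-of-infection model. Those last two need not condition on infection. All of this stands, and it limits the weight of the point. It does not remove the mismatch with the section's opening question, or with the caution in 5.5.4.5.

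A reader might infer more than the documents support:
- That every test in the section rejects often. Only the proportional odds test was computed, and the inflation comes mainly from the asymptomatic category. Symptom scores and time to resolution were not simulated.
- That the inflation is unconditional. It needs efficacy to vary with would-be severity through prevention. Attributing the whole Table 4 gradient to prevention is an extreme case.
- That the SAP states a null hypothesis about people who would be infected in either arm. It does not; the causal reading comes from the introductory sentence.
- That the patient-reported mean differences carry p-values. They are descriptive. The Markov comparison is optional and the log-rank test is to be used where applicable.

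**Conclusion.** The point holds in this form. The proportional odds, Markov and log-rank comparisons, and the descriptive patient-reported contrasts, condition on infection and cannot separate softening from selective prevention. For the proportional odds test, false rejection at 154 moderate or severe events is about 53% to 95% under the Table 4 efficacies acting wholly by prevention, about 19% with a small gradient, about 10% among symptomatic cases only, and 5% with equal efficacy. These figures rest on the two-sided 5% level, Poisson counts, full detection of asymptomatic infection and the assumed mechanism. The SAP treats the same problem properly for viral load and not here. No primary or confirmatory secondary conclusion is affected. It is a cheap improvement to an exploratory section.

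**What to change.** In section 5.6.1.3:

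1. State that the unadjusted p-values compare case mix among infected participants and do not by themselves show that the vaccine softens infection; cross-refer to the caution in 5.5.4.5.
2. Extend the selection-bias sensitivity analysis of 5.5.4.5 to the ordinal severity category and, where feasible, to the symptom scores. Plot the effect and its confidence interval against b, and report the b at which the effect disappears.
3. Attach no pass/fail rule over a range of b. Because softening and selection can give the same expected counts, a rule requiring the effect to persist across a range that includes the matching slope would almost never support a true attenuation.
4. Rest conclusions about severity on the severity-specific VE in the whole per-protocol set (5.5.4.2, Appendix 8).

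The cost is SAP wording plus some programming, since the planned code is for viral load and must be adapted to an ordinal outcome. Time to resolution would need further adaptation for censoring. The exploratory claim may also become weaker.
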